6 INTRODUCTION

6.1 Background

Sweden has the lowest prevalence of smoking in Europe, particularly among males. It is widely accepted that one contributory factor to this trend is that snus has replaced cigarettes as the tobacco product of choice among many males and some females.

The nicotine delivery profile of a product is probably one of the main determinants of its efficacy to decrease nicotine craving and, thus, its ability to function as an alternative to cigarettes among current smokers. Oral tobacco, such as snus, is capable of effectively delivering nicotine to the bloodstream through diffusion over the oral mucosa [1]. It may therefore be more satisfactory to smokers than currently available pharmaceutical nicotine replacement therapies (NRTs) with a slower nicotine-delivery profile. Orally administered nicotine, whether in the form of snus or NRT, can never achieve the rapidly rising and very high nicotine levels in the arterial blood to the brain that is typically associated with pulmonary delivery resulting from inhalation of tobacco smoke.

Use of oral tobacco is by definition unassociated with exposure to the many thousands of combustion compounds found in tobacco smoke (many of which are highly carcinogenic and may induce a state of systemic, chronic inflammation), or chronic irritation in the upper and lower airways resulting from the inhalation of tobacco smoke. Therefore, it is generally accepted that use of oral tobacco products has substantially lower health risks than cigarette smoking.

Nicotine is the substance that is the major contributor to the addictive properties of tobacco products, and nicotine exposure may contribute to adverse pregnancy outcomes. In addition, oral tobacco products typically contain low levels of unwanted substances (including nitrosamines and polycyclic hydrocarbons) that have been classified as human carcinogens. So, although the health effects are substantially smaller for oral tobacco compared to cigarette smoking, some adverse effects cannot be ruled out, particularly the effects related to the nicotine exposure.

Traditionally there has been no non-tobacco-based nicotine product intended for recreational use. Despite the vast risk differential between snus and cigarettes in terms of adverse long-term health effects, snus remains a controversial product as it contains tobacco, is intended for recreational use, and is potentially addictive. The tobacco component of snus explains why it contains measurable amounts of unwanted, potentially carcinogenic constituents, albeit at very low concentrations. Oral tobacco-derived nicotine (OTDN) products (*e.g.*, ZYN) have been commercially available for a few years. They have some features that are similar to snus as they come in pouches that are intended to be placed under the upper lip. However, in contrast to snus, these products contain no nitrosamines or polycyclic hydrocarbons, which are the two main classes of unwanted substances in snus. The nicotine content in ZYN (1.5-13 mg/unit) is comparable to that in snus and many other oral tobacco products that are currently common on the market in Scandinavia and the United States, which have nicotine contents ranging from 3 mg/unit to more than 20 mg/unit.

CONFIDENTIAL 17 (59)

When comparing the nicotine content of different nicotine-delivery products, it is important to consider that the nicotine extraction and uptake varies considerably depending on product type (tobacco *vs.* a non-tobacco-based matrix) and product formulation (pouch geometry, solubility, water content, particle size, pH, etc.). In addition, there is a substantial inter-individual variation in uptake for products used orally, which is probably related to constitutional differences in saliva production, for example, and results in a wide variation in nicotine extraction.

Previous studies [2] have found that General PSWL (snus) and ZYN Dry release approximately 32-33% and 50-60% of the nicotine during 60 min, respectively, although with large interindividual variation. Extraction is generally larger for small pouches compared to larger pouches, which suggests that surface area, saliva penetration and diffusion factors may be more important determinants of nicotine uptake than pouch weight.

While numerous OTDN products are currently commercially available, only a limited number of these products have, thus far, been scientifically evaluated. It has been suggested that some flavors may enhance nicotine uptake, which has not been fully scientifically investigated for this product category. Similarly, there is a lack of scientific data regarding any possible impact of flavors on pharmacodynamics (PD). Further, the addition of flavors to tobacco products and e-cigarettes have been discussed by regulatory agencies during the last years. The World Health Organization (WHO) seventh report on the scientific basis of tobacco product regulation included a chapter on flavors [3]. Additionally, the United States Food and Drug Administration (FDA) is stressing the need to investigate the effect of flavors on the pharmacokinetics (PK) and PD of nicotine products, as well as a guidance [4] outlining the importance of PD outputs in such investigations.

This study is a part of the effort by Swedish Match to assess if flavoring affects the nicotine uptake, PK and PD of ZYN Dry products. ZYN Dry products have a different product formulation compared to ZYN ULTRA products, for which Swedish Match recently conducted a similar study (study code SM20-02). ZYN ULTRA has a larger pouch dimension and higher moisture, salt, and nicotine content than ZYN Dry which, as mentioned above, may affect nicotine extraction and uptake. While the general PK characteristics of nicotine are known, the nicotine delivery, uptake and subsequent exposure associated with use of ZYN Dry are not. By this approach, the study enables a solid scientific evaluation of the PK and PD properties of ZYN Dry, which will have implications for the assessment of the overall safety profile associated with this emerging product category *vs.* other nicotine products. Given the lack of data on the possible impact of the flavors on the delivery and experience of nicotine in OTDN products, the results generated from this study should be of interest not only for the tobacco industry and consumers, but also for lawmakers and the relevant regulatory authorities. The results of the study will also be made available in the public domain to enhance awareness among these key stakeholders.

The results from this study are intended to be used as a basis in a premarket tobacco product application (PMTA) to the FDA. Prior to introduction and marketing of novel nicotine-based products in the United States, the FDA specifically requires data on nicotine uptake and nicotine effects in order to assess health risks and addiction potential of the new tobacco/nicotine-containing products as compared to existing ones.

6.2 Study rationale

The overarching aim of the study is to evaluate the impact of flavors on nicotine uptake from ZYN Dry products. The rationale for the study design is presented in Section 8.2.

CONFIDENTIAL 18 (59)

6.3 Risk/benefit assessment

6.3.1 Risk assessment

It may be considered problematic to expose research subjects to a novel nicotine delivery product with properties that are not yet fully known. However, all research subjects are required to be daily oral tobacco/nicotine pouch users since at least one year (with an average or above-average pouch consumption). Thus, the participants are well acquainted with and used to the effects of nicotine, and there will be no risk for the development of any novel nicotine dependency among the participants.

The nicotine in the OTDN products is of pharmaceutical grade, same as the nicotine used in NRT products (*e.g.*, gum, lozenges, mouth spray etc.). Aside from the nicotine, all ingredients used in the OTDN products are approved for use in food.

The potential adverse effects of the study procedures are likely to be minor and/or clinically insignificant, based on experience from clinical trials on similar products [5-8]. The evidence on the health effects of nicotine exposure is based on existing tobacco products. In addition, any potential subject who intends to change their nicotine consumption habit or stop using nicotine products will not be offered the opportunity to participate in the study. Consequently, the present study is not perceived to confer any societal burden in terms of increased use of tobacco or OTDN products.

Pregnant and breastfeeding subjects, and individuals with a history of hypertension or any cardiovascular disease, who may be particularly vulnerable to nicotine exposure, are also excluded from participation.

Each unit of IP (one pouch) will be used for 60 min per study day (see Section 8.1). The subjects will not be exposed to nicotine levels from the IPs that are higher than those they are usually exposed to during their daily consumption of nicotine. Therefore, acute risks related to the IP administration are anticipated to be low. So far, no adverse events (AEs) have been reported in previous clinical studies with similar products, apart from effects likely to be related to the nicotine exposure (such as salivation, nausea, and dyspepsia).

The PI at the research clinic will ascertain adequate facilities and procedures are available to handle any emergency situations that may occur during the study. The medical staff at CTC have extensive experience in clinical studies and there are adequate procedures in place to handle unexpected and expected adverse reactions.

Aside from the risks related to the IPs, there may also be risks related to the medical devices used in the study (*e.g.*, indwelling venous catheters). However, these are devices that are used in routine medical care and the risk associated with their use is considered low and ethically justifiable. Study specific evaluations and sampling procedures, like blood-pressure measurements using a blood pressure cuff and frequent blood-sampling, may cause transient discomfort but the risk is deemed to be low and ethically justifiable.

The potential AEs of the study procedures, which are likely to be minor and/or clinically insignificant, are from a research ethics perspective, counterbalanced by substantially reduced harm and risk of tobacco-related diseases of the novel OTDN pouches. As the nicotine delivery profile of a product is likely to be central to its acceptability among current nicotine users, it is reasonable to conduct formal clinical studies to assess this feature in more detail.

CONFIDENTIAL 19 (59)

6.3.2 Benefit assessment

In analogy with a regular phase I study in healthy volunteers, there is no direct benefit for the subjects to participate in the study, aside from a brief medical examination, which may provide them with information on their general state of health. Hence, the safety and wellbeing of the subjects are of outmost importance.

The development of new, nicotine-containing products takes place both in the pharmaceutical industry and in the tobacco industry. Parts of the tobacco industry today are moving towards reducing the presence of known harmful substances, other than nicotine, in the products that are being developed. OTDN products are an example of such a development, and the use, prevalence and variety of these products has increased globally in recent years. OTDN pouches constitute a substitute to both combusted or non-combusted tobacco/nicotine-containing inhalation products (*e.g.*, conventional cigarettes, heated tobacco vaporizers or electronic cigarettes) and to oral tobacco products (*e.g.*, tobacco-based snus and moist snuff).

As mentioned in Section 6.1 above, there is a lack of scientific data regarding the potential effects of flavoring on nicotine uptake, PK and PD for oral nicotine products in general. Thus, the results generated from this study should be of interest not only for the tobacco industry and consumers, but also for lawmakers and the relevant regulatory authorities.

6.3.3 Risk/benefit conclusions

It is reasonable to assume that OTDN products will have less harmful effects on health than tobacco-based nicotine products. From that perspective, the aim of the present study is consistent with society's overall goal of reducing the harm caused by tobacco use.

Overall, the potential benefit of developing and thoroughly characterizing improved tobacco-leaf free nicotine preparations is considered to outweigh the minimal risks that the subjects are exposed to in the study.

6.4 Risk assessment with regard to the COVID-19 pandemic

Current recommendations from the authorities will be considered on a day-to-day basis and a continuous risk evaluation will be made to assess how the COVID-19 pandemic is affecting the study conduct and the safety of the study subjects. This study is a short-term study including a healthy population. Hence, study participation should not contribute to increased risks on behalf of the safety of the study subjects or the quality of the data collected.

The recommendations from the European Medicines Agency (EMA) [9,10] as well as the Swedish Medical Products Agency (MPA) [11] regarding the conduct and management of clinical trials during the COVID-19 pandemic will be taken into consideration. Currently identified risks as well as the planned prevention and mitigation actions are detailed in Table 6.4-1 and in a risk log as part of the Sponsor's trial master file (TMF). These may be updated in line with prevailing recommendations, as applicable.

CONFIDENTIAL 20 (59)

Table 6.4-1 COVID-19 related risks and mitigating actions

Risks identified	Actions
Subjects will be exposed to the SARS-CoV-2 virus, which may lead to subsequent development of COVID-19.	According to CTC's policy, which is based on the recommendations by the Public Health Agency of Sweden (Folkhälsomyndigheten), subjects are not allowed to visit the clinic if they have any symptoms (even if not COVID-19 related). Subjects are contacted before visits to ensure they do not have any symptoms, and at each visit the subjects' health status is verified before letting them enter the study site.
	Subjects are supplied with hand disinfectant to use during visits to the clinic.
	The study site has elevated the level of cleaning to include regular disinfection of all surfaces in the clinic and clinic kitchen.
Subjects will fall ill with	AEs will be followed up by phone.
OVID-19 between visits and ot be able to show up for IP	Subjects with suspected COVID-19 symptoms will be directed to seek COVID-19 testing.
administration and study assessments within the assigned time window.	Subjects who are tested positive for COVID-19 between visits will be referred to standard hospital care if needed.
Subjects will fall ill with COVID-19-like symptoms during a visit to the study site.	There is a clear action plan if a subject becomes ill during a site visit. The subject is isolated, and if no safety reasons are identified, the subject is sent home and carefully followed up on by site staff. If the subject cannot be sent home because of safety reasons, the subject is isolated and site staff who are in contact with the subject have to wear appropriate personal protective equipment (PPE). The PI will contact the nearest infection clinic and decide on further actions.
The hospital laboratory will not be able to analyze safety samples due to the number of COVID-19 samples.	An accredited laboratory has been contracted as a back-up for the analysis of safety samples.
New recommended actions by health authorities that may halt the study, such as society lock- down, if the pandemic escalates	This risk does not affect subject safety.
There will be an increased number of protocol deviations due to the COVID-19 pandemic.	All protocol deviations will be handled according to CTC's standard operating procedures (SOPs).

CONFIDENTIAL 21 (59)

7 STUDY OBJECTIVES AND ENDPOINTS

7.1 Primary objective

The primary objective of the study is to evaluate the impact of flavor on nicotine exposure, after the administration of single doses of unflavored ZYN Dry Smooth 6 mg and flavored ZYN Dry Virginia Blend 6 mg.

7.1.1 **Primary endpoint**

PK of nicotine in plasma: The equivalence (90% confidence interval for the ratio between 0.8 and 1.25) in the baseline-adjusted area under the curve from 0 to infinity (AUC_{inf}) based on nicotine plasma concentrations after the administration of single doses of unflavored ZYN Dry Smooth 6 mg and flavored ZYN Dry Virginia Blend 6 mg.

7.2 Secondary objectives

The secondary objectives of the study are:

- 1. To compare the *in vivo* extracted amount (mg/unit) and extracted fraction (%) of nicotine between the unflavored and flavored ZYN Dry products.
- 2. To compare the PK profile between the unflavored and flavored ZYN Dry products.
- 3. To evaluate the impact of flavors on PD effects, measured as the pulse rate and subjective outcome measures, for all the ZYN Dry products.
- 4. To evaluate the safety and tolerability of ZYN Dry products in current, daily oral tobacco/nicotine users.

7.2.1 Secondary endpoints

The secondary endpoints are:

- 1. The difference in *in vivo* extracted amount (mg/unit) and extracted fraction (%) of nicotine between the unflavored and flavored ZYN Dry products.
- 2a. PK of nicotine in plasma: The equivalence between the unflavored and flavored ZYN Dry products in the non-adjusted and baseline-adjusted PK parameters maximum observed concentration (C_{max}) and AUC_{inf} based on plasma concentrations of nicotine after the administration of single doses.
- 2b. PK of nicotine in plasma: The difference between the unflavored and flavored ZYN Dry products in the non-adjusted and baseline-adjusted PK parameters time of occurrence of $C_{max}(T_{max})$, area under the curve from 0 to 1.5 h (AUC_{0-1.5h}), and AUC from 0 to the last measurable time point (AUC_{0-last}).
- 3a. The difference between the unflavored and flavored ZYN Dry products for the highest recorded increase (E_{max}) in pulse rate from baseline, measured using a pulse oximeter after IP administration.
- 3b. The difference between the unflavored and flavored ZYN Dry products for the highest recorded increase (E_{max}) in the subjective parameters "craving" and "satisfaction" measured using a 100 mm visual analogue scale (VAS) after IP administration.

CONFIDENTIAL 22 (59)

- 3c. The difference between the unflavored and flavored ZYN Dry products for the subjective parameters "product-liking" and "intent to use again", measured using a 100 mm VAS 60 min after IP administration.
- 4. Frequency, intensity, and seriousness of AEs.

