- 1. The difference in *in vivo* extracted amount (mg/unit) and extracted fraction (%) of nicotine between the unflavored and flavored ZYN Dry products.
- 2a. PK of nicotine in plasma: The equivalence between the unflavored and flavored ZYN Dry products in the non-adjusted and baseline-adjusted PK parameters C_{max} and AUC_{inf} based on plasma concentrations of nicotine after the administration of single doses.
- 2b. PK of nicotine in plasma: The difference between the unflavored and flavored ZYN Dry products in the non-adjusted and baseline-adjusted PK parameters time of occurrence of C_{max} (T_{max}), the area under the curve from 0 to 1.5 h (AUC_{0-1 5h}), and the AUC from 0 to the last measurable time point (AUC_{0-last}).
- 3a. The difference between the unflavored and flavored ZYN Dry products for the highest recorded increase (E_{max}) in pulse rate from baseline, measured using a pulse oximeter after IP administration.
- 3b. The difference between the unflavored and flavored ZYN Dry products for the highest recorded increase (E_{max}) in the subjective parameters "craving" and "satisfaction", measured using a 100 mm visual analogue scale (VAS) after IP administration.
- 3c. The difference between the unflavored and flavored ZYN Dry products for the subjective parameters "product-liking" and "intent to use again", measured using a 100 mm VAS 60 min after IP administration.
- 4. Frequency, intensity, and seriousness of adverse events (AEs).

Exploratory endpoints

- 1. The difference in "product-liking" *vs.* the subjects' usual oral tobacco/nicotine product of choice between the unflavored and flavored ZYN Dry products, measured on a 3-point scale using a multiple-choice question (MCQ) 60 min after IP administration.
- 2. The difference in nicotine extraction-normalized AUC_{inf} and C_{max} between the unflavored and flavored ZYN Dry products.

Number of subjects planned

Approximately 63 subjects will be screened with the aim to achieve 42 randomized subjects and 36 fully evaluable subjects. A fully evaluable subject is defined as a subject who has received all 9 IPs and who has completed all study visits. An effort will be made to randomize at least 17 female subjects (approximately 40 %).

Diagnosis and main eligibility criteria

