FDA Food and Drug Administration GCP Good clinical practice GDPR General data protection regulation HIV Human immunodeficiency virus HR Heart rate ICF Informed consent form ICH International Council for Harmonisation of Technical Requirements for Pharmaceuticals for Human Use	E_{max}	Highest recorded change from baseline
GCP Good clinical practice GDPR General data protection regulation HIV Human immunodeficiency virus HR Heart rate ICF Informed consent form ICH International Council for Harmonisation of Technical Requirements for Pharmaceuticals for Human Use	FAS	Full analysis set
GDPR General data protection regulation HIV Human immunodeficiency virus HR Heart rate ICF Informed consent form ICH International Council for Harmonisation of Technical Requirements for Pharmaceuticals for Human Use	FDA	Food and Drug Administration
HIV Human immunodeficiency virus HR Heart rate ICF Informed consent form ICH International Council for Harmonisation of Technical Requirements for Pharmaceuticals for Human Use	GCP	Good clinical practice
HR Heart rate ICF Informed consent form ICH International Council for Harmonisation of Technical Requirements for Pharmaceuticals for Human Use	GDPR	General data protection regulation
ICF Informed consent form ICH International Council for Harmonisation of Technical Requirements for Pharmaceuticals for Human Use	HIV	Human immunodeficiency virus
ICH International Council for Harmonisation of Technical Requirements for Pharmaceuticals for Human Use	HR	Heart rate
Requirements for Pharmaceuticals for Human Use	ICF	Informed consent form
IEC Independent ethics committee	ICH	
	IEC	Independent ethics committee
IME Important medical event	IME	Important medical event

CONFIDENTIAL 11 (59)

IUS

IP Investigational product

ISF Investigator site file
IOR Interquartile range

IUD Intra-uterine device

Lambda_z Estimate of the terminal elimination rate constant

Intra-uterine system

LC-MS Liquid chromatography-mass spectrometry

LLOQ Lower limit of quantification

LSMeans Least-squares means

MCQ Multiple-choice question

MedDRA Medical dictionary for regulatory activities

MPA Medical Products Agency

MS Mass spectrometry

NCA Non-compartmental analysis

NRT Nicotine replacement therapies

OTDN Oral tobacco-derived nicotine

PD Pharmacodynamic(s)
PI Principal Investigator

PII Personally Identifiable Information

PK Pharmacokinetic(s)
PKAS PK analysis set

PMTA Premarket tobacco product application

PPE Personal protective equipment

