11.4.2.2 Subjective parameters

Subjective parameters ("craving", "satisfaction", "product-liking" and "intent to use again") will be rated using VAS, anchored with "not at all" to "extremely", or "very likely" for the "intent to use again" parameter.

The "craving" parameter will be assessed with the question "Right now, how strong is your urge to snus?" at the same pre-defined time points as the pulse-rate assessments: -10 min prior to IP administration, and 5 min, 10 min, 15 min, 30 min, 45 min, 60 min, 1 h:15 min, 1 h:30 min, 2 h, 4 h, and 6 h post-administration.

The "satisfaction" parameter will be assessed with the question "Right now, is the product satisfying?" at the pre-defined time points: 5 min, 10 min, 15 min, 30 min, 45 min, 60 min, 1 h:15 min, 1 h:30 min, 2 h, 4 h, and 6 h post-administration.

In addition, "product-liking" and "intent to use again" parameters will be assessed at 60 min post-administration with the questions "How much did you like the product?" and "How likely are you to use this product again in the future?", respectively.

Time points for each of the VAS questions are outlined in Table 8.1-2, and allowed deviations from actual time are outlined in Table 11.1-1.

11.4.3 *Nicotine extraction from pouches*

Used pouches will be collected after 60 min (+/- 1 min) of use for the determination of residual nicotine in the IPs.

All the collected pouches will be frozen immediately at -20°C. Pouches for extraction of nicotine will be analyzed by Swedish Match.

CONFIDENTIAL 38 (59)

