17.7.3 Pharmacodynamic effects of ZYN Dry

The analyses of pulse rate as a measure of the PD effect of nicotine will be further described in the SAP. Data will be presented as summary tables of descriptive statistics and plots of pulse rates over time for each IP.

The subjective parameters "craving", "satisfaction", "product-liking" and "intent to use again", measured by VAS, will be summarized for each IP using descriptive statistics as a total score during the IP administration phase. The relative and absolute change from baseline will also be calculated for the subjective parameter "craving" for each IP.

To determine the maximum PD effect attributable to the IP, the E_{max} as well as time to first instance of E_{max} will be calculated for the pulse rates as well as for the subjective parameter "craving". For the subjective parameter "satisfaction", which does not have a baseline, the maximum value will be recorded as E_{max} along with time to E_{max} .

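### Secondary endpoint 3b scores craving by its highest increase, although the effect of interest is a decrease, so it picks the rating with the least relief

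*Protocol*

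**What the plan says.** Protocol Section 7.2.1, endpoint 3b, compares the unflavored and flavored products "for the highest recorded increase (E_{max}) in the subjective parameters 'craving' and 'satisfaction". The synopsis says the same: "highest recorded increase (E_{max}) in the subjective parameters". One definition covers both parameters.

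Section 11.4.2.2 gives the craving question as "Right now, how strong is your urge to snus", on a 100 mm VAS "anchored with 'not at all' to 'extremely". A higher score is therefore a stronger urge. The baseline rating is at −10 min, followed by 11 ratings from 5 min to 6 h. Sections 8.1 and 9.6.1 require at least 12 h without nicotine before the visit, and 9.6.1 extends this through the visit. The pouch is in place for 60 min (10.5).

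Three other places bear on direction:

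- Section 6.1 describes the property of interest as a product's "efficacy to decrease nicotine craving".
- Section 17.7.3 calculates Emax, and time to its first instance, for pulse rate and craving: "To determine the maximum PD effect attributable to the IP". It gives satisfaction, which has no baseline, its own rule (the maximum value). It also plans further craving summaries by product: "The relative and absolute change from baseline will also be calculated".
- The abbreviation list (Section 3) defines Emax as "Highest recorded change from baseline", without a direction.

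**The concern.** An increase is the natural direction for pulse rate, and a maximum is natural for satisfaction. Craving runs the other way: a subject arrives after overnight abstinence and the pouch is expected to lower the urge. Applied to craving, the definition in 3b returns the least favorable post-administration rating. Time to Emax then marks when the pouch did least.

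Secondary objective 3 asks how flavors affect PD, and Section 6.1 says the results are meant to support a PMTA. A flavor that changed craving relief could show little difference on the endpoint meant to detect it. An SAP that follows the protocol carries this forward. One that reverses it departs from a stated secondary endpoint.

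**Working it through.** The protocol gives no effect size, expected profile or sample size for craving, so there is no figure to reproduce on this point. The 36 evaluable subjects in Section 17.2 concern AUCinf equivalence only.

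**1. What the rule selects.** This step needs no assumption about the time course. Let *b* be the rating at −10 min, *y(t)* the rating at each of the 11 later times, and relief *r(t) = b − y(t)*.

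- As written: Emax = max[*y(t) − b*] = −min[*r(t)*], the smallest relief with its sign changed.
- Effect of interest: max[*r(t)*] = *b* − min[*y(t)*], the largest relief.

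If every later rating is below baseline, Emax as written is negative.

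**2. A hand example (assumed values).** Baseline is 60 mm, the lowest rating is 25 mm at 60 min, and the highest is 68 mm at 6 h.

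- As written: 68 − 60 = +8 mm, at 360 min.
- Largest decrease: 60 − 25 = 35 mm, at 60 min.
- A second product with about half the relief (lowest rating 43 mm, 60 − 43 = 17 mm) and the same 6 h rating also scores +8 mm. The tie follows from assuming the same 6 h value.

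**3. A simulation (all curves assumed).** Two products with true peak relief of 20 and 40 mm were compared at the protocol's 11 times. Mean relief was 20% of its peak at 5 min, 50% at 15 min, 100% at 60 min and 70% at 2 h. The mean 6 h rating was set at −5, 0 or +10 mm from baseline. Baseline means were 50, 60 and 75 mm (SD 15), measurement SD was 8 mm, the SD of the late shift between subjects was 10 mm, and ratings were held within 0 to 100. Each product and setting had 40,000 profiles. For a baseline mean of 60 mm:

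| Mean 6 h rating vs baseline | Highest increase, 20 / 40 mm product | Gap | Largest decrease, 20 / 40 mm product | Gap |
|---|---|---|---|---|
| −5 mm | 4.4 / 0.7 | 3.7 | 28.3 / 44.4 | 16.1 |
| 0 mm | 6.5 / 3.6 | 2.9 | 28.1 / 44.4 | 16.4 |
| +10 mm | 12.1 / 10.7 | 1.4 | 27.9 / 44.4 | 16.6 |

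Gaps were taken before rounding. Over all nine settings the gap is 1.3 to 3.8 mm on highest increase and 13.8 to 17.9 mm on largest decrease. Within a setting, the first is between 1.3/17.9 = 7% and 3.8/13.8 = 28% of the second.

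**4. Where the highest increase falls in these profiles.** It falls at 4 to 6 h in about 38 to 87%, at 5 min in about 9 to 32%, and is zero or negative in about 16 to 51%. For the 40 mm product, the largest decrease falls between 15 min and 2 h in at least 98%.

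**5. Can another passage be read as correcting 3b?** Section 17.7.3 states a purpose but no direction. The abbreviation list says change, which can mean the algebraic maximum or the largest magnitude. Nowhere is Emax for craving defined as a decrease, and 3b says increase in two places.

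**The case against.** The strongest case on the other side concedes the wording of 3b and disputes its reach.

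- **Section 17.7.3 is not itself wrong.** It never says increase. With the undirected glossary entry, it is compatible with a largest decrease. This stands: the conflict is between 3b and the purpose in 17.7.3.
- **Craving relief is summarized elsewhere.** The planned absolute and relative changes from baseline could show a fall in craving. This stands as a limit on the damage. Those summaries are descriptive and by product, and do not redefine the comparison in 3b.
- **The endpoint cannot be said to measure late withdrawal.** A reader might infer this from the 12 h abstinence, 60 min of use and ratings to 6 h. The protocol gives no craving time course, and on the assumed profiles the highest increase can also fall in the first minutes. Only the time of least relief is supported.
- **Wrong ranking is not shown.** A reader might infer that products would be ordered wrongly. The hand example gives a tie and the simulation a compressed gap. In the simulation, the product with more relief has the smaller increase, so the order holds if a smaller increase is read as better.
- **Detail may be left to the SAP.** This does not stand as a defence. The protocol states a direction, and it is the wrong one for this scale.
- **The reach is small.** It is one parameter of one secondary endpoint. All ratings are kept, and no success criterion rests on craving. This stands and lowers the priority.

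**Conclusion.** The point holds as an error of definition in endpoint 3b. On this scale the highest increase is, by algebra, the smallest relief with its sign changed. It is opposite in direction to the effect named in Section 6.1 and does not serve the purpose stated in Section 17.7.3. Time to Emax for craving inherits the problem if 3b's direction is applied.

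The size is illustrative. On the assumed profiles, a true 20 mm difference in peak relief shrinks to 1.3 to 3.8 mm, against 13.8 to 17.9 mm on the largest decrease. These are gaps in means, without a comparison of variability, so they do not translate into a loss of power.

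The documents do not support saying that the study's craving data as a whole are uninformative. Pulse rate, satisfaction, the primary endpoint, the sample size and data collection are unaffected. This should be fixed before database lock, but it does not threaten the trial's main conclusion.

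**What to change.** Define Emax for craving as the largest decrease from the −10 min rating, that is, baseline minus the lowest post-administration rating, with positive values meaning relief. Define time to Emax for craving as the time of the first occurrence of that lowest rating. Keep highest increase for pulse rate and maximum value for satisfaction.

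Align four places: the synopsis (3b), Section 7.2.1 (3b), the Emax entry in the abbreviation list, which should say that direction depends on the parameter, and Section 17.7.3.

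The cost is wording only, in a numbered amendment as Section 14.5 requires. Every rating needed is already scheduled, and the sample size does not change. Settling it before database lock avoids choosing the direction after results are seen.
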